### 8.2.1.2. Methods of tumor assessment

The choice of the imaging method for tumor assessment is taken by the site, based on local feasibility and clinical adequacy. However, the same method of assessment and the same technique must be used throughout the trial for any given patient. Extent of disease evaluation by institutional guidelines per RECIST includes CT scan with IV contrast of the thorax, abdomen, and pelvis as well as other anatomical areas as appropriate (i.e., CNS imaging for symptomatic SCLC patients, if appropriate). Of note, all known or suspected disease-involved areas assessed at screening should be at least, included in all subsequent assessments. MRI may be used to assess sites of disease not adequately imaged by CT or in patients known to have an allergy to iodine-containing contrast or moderate to severe renal impairment (calculated creatinine clearance  $< 50$  ml/min).

For Cohort 4 exclusively, extent of disease evaluation by the GCIG criteria includes a monthly dosage of the serum tumor marker CA-125, if applicable, in patients without RECIST measurable disease in ovarian cancer, fallopian cancer, PPC, and/or endometrial cancer with elevated CA-125.

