#### 8.3.2.1. End of treatment

Treatment with Debio 1143 will be continued until any of the following occurs:

1. Unacceptable toxicity [including, treatment-related NCI-CTCAE v5.0 grade 4 laboratory abnormalities (excluding hematological and/or non-febrile asymptomatic neutropenia/leukopenia)] that does not resolve with appropriate standard medical measures; or intercurrent illness that would, in the opinion of the Investigator, affect assessments of clinical status to a significant degree or compromise the patient's safety;
2. Permanent discontinuation of nivolumab;
3. Treatment delay greater than 4 and 8 weeks (+1-week tolerance) for Debio 1143 and nivolumab, respectively;
4. Need to discontinue Debio 1143 due to toxicity despite dose reduction to 100 mg/d;
5. Prohibited medication as indicated in [section 7.7.2](#) is required/used during the course of the trial. In the event a patient is found to be taking a prohibited medication during the trial, the site should immediately contact the medical monitor. The decision to withdraw the patient will be made in conjunction with the Sponsor;
6. If a critical protocol violation occurs that may preclude safety continuation of the study for the patient, the Sponsor's trial manager will be contacted to discuss if the patient has to be withdrawn from treatment;
7. Symptomatic disease progression documented by RECIST v1.1 or by GCIG criteria (Cohort 4, if applicable) in RECIST non-evaluable patients. However, patients may continue study treatment if, in the Investigator's opinion, there is reasonable evidence of ongoing clinical benefit or suggestion of "pseudoprogression" without excess risk of toxicity or complications for the patients.
8. Confirmed disease progression as per iRECIST;
9. Any medical condition that the Investigator or Sponsor determines may jeopardize the patient's safety if he or she continues in the study;
10. Withdrawal of patient's consent;
11. Pregnancy or breast-feeding a baby;
12. Start of any subsequent anti-neoplastic therapy (excluding palliative symptomatic localized RT up to 36 Gy total doses for alleviating symptoms e.g. pain, intracranial hypertension, which may continue upon the Sponsor's agreement, if appropriate). These patients will continue only in the OS follow-up.

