#### **11.4.1. Derived parameters and endpoints**

##### **11.4.1.1. Efficacy**

Patients without any new anticancer therapy or PD will be assessed for anti-tumor efficacy every 8 weeks (±1 week) during the first 10 cycles and then every 12 weeks (± 1 week) from Cycle 13 onwards until PD occurs or start of a new cancer treatment or end-of-life-care or until the end of the Main study period whichever occurs first. For patients who continue study treatment after the Main study period, tumor

response assessments will continue at the frequency of local institutional care practice until PD, start of any new anti-cancer therapy, death or EOT, whichever occurs first.

Response according to RECIST version 1.1 (38) or GCIG criteria (39) (Cohort 4 for RECIST non-evaluable patients) will be assessed in the efficacy and ITT populations. CR and PR must be demonstrated by objective tumor assessment (CT scan/MRI or CA-125 dosage) and confirmed 4 weeks later. All patients will have a CT scan/MRI or CA-125 dosage at the time of PD. Tumor response will also be assessed by using the novel modified RECIST v1.1 guideline for immunotherapeutics, iRECIST.(40) These exploratory analyses using iRECIST guideline will be presented in detail in the SAP.

In case of premature discontinuation with SD at the EOS visit, this SD will be included in the derivation of efficacy parameters only if the assessment has been performed at least 35 days after treatment start.

The start of a systemic new anti-cancer therapy without prior disease progression could potentially impact the tumor activity observed, hence potentially biasing the evaluation of Debio 1143 anti-tumor activity. As a consequence, no further efficacy data will be collected after the start of any new anti-cancer treatment, except for OS, at least until study data cut-off.

The confirmed response will be used in the primary ORR analysis while a secondary analysis will be performed using the unconfirmed response.

- **Objective response** is derived as any PR or CR recorded after the start of study treatment until disease progression/recurrence is documented, a new systemic anti-cancer therapy is started or analysis cut-off, whichever occurs first.
- **BOR** is the best response (CR, PR, stable disease or disease progression) recorded after the start of study treatment until disease progression/recurrence is documented, a new systemic anti-cancer therapy is started or analysis cut-off, whichever occurs first.

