##### Definition of PFS and duration of response by CA-125

PFS based on CA-125 will be defined as the time from first study drug infusion until the GCIG-Rustin-modified criteria of progression are met, or until the date of death (with or without disease progression). Duration of CA-125 response will be defined as the time between when the CA-125 was first documented to have decreased by 50% in a patient who meets all the GCIG-Rustin-modified criteria for a CA-125 response, and the time the CA-125 is first documented to have risen to the point where the patient meets GCIG criteria of disease progression.

GCIG-Rustin-modified definition of progressive disease according to CA-125 criteria		
	Definition of progression	Date of progression
Patients with elevated CA-125 before treatment and normalization of CA-125 during treatment	CA-125 $\geq$ 2 X ULN documented on 2 occasions**	Date CA-125 is first elevated to $\geq$ 2 X ULN
Patients with elevated CA-125 pretreatment that never normalizes	CA-125 $\geq$ 2 X nadir value on 2 occasions**	Date CA-125 is first elevated to $\geq$ 2 X nadir value
Patients with CA-125 in normal range pretreatment	CA-125 $\geq$ 2 X ULN documented on 2 occasions**	Date CA-125 is first elevated to $\geq$ 2 X ULN

\*\*Repeat CA-125 anytime but normally not less than 1 week after the first elevated CA-125 level. CA-125 levels in samples obtained after administration of mouse antibodies or within 4 weeks after surgery or paracentesis should not be taken into account.

In patients for whom response to treatment is evaluated by both RECIST and CA-125 criteria, the date of response and progression will be the earliest date of the two methods.

¶Adapted from Rustin et al, 2004 (41)

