17.1.1. PRIMARY EFFICACY VARIABLE & DERIVATION

The primary efficacy variable is confirmed ORR as per RECIST v1.1 and/or CGIG criteria (cohort 4, if applicable).

Confirmed objective response as per RECIST v1.1 is a confirmed best overall response (cBOR) of partial response (PR) or complete response (CR). The full derivation of confirmed BOR is included in Section 17.2.1.2.

In the situation of lack of RECIST evaluation data (cohort 4 only), confirmed objective response as per GCIG criteria will be done using CA-125 levels. Patients will be scored as having attained a CA-125 response if they meet the GCIG-Rustin-modified criteria which require that there is at least a 50% reduction in CA-125 levels from a pre-treatment sample. The response must be confirmed and maintained for at least 28 days. Patients can be evaluated according to CA-125 only if they have a pre-treatment sample that is at least twice the upper limit of normal and within 2 weeks prior to starting treatment.

Document: T:\sas\Debiopharm\Debio_1143\CZA60507\Biostatistics\Documentation\SAP\SAP Text\V5

Author: [REDACTED] Version Number: 5.0
Version Date: 19APR2022

Template No.: CS_TP_BS016 Revision 5
Effective Date: 01Apr2018

Reference: CS_WI_BS005

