17.2.1.5. Progression-free survival (PFS)

PFS (months) is defined as (date of the first documented disease progression or death due to any cause, whichever occurs first – start date of treatment + 1)/30.4375.

The following censoring rules will be applied:

Situation	Date of Progression or Censoring	Outcome
No baseline and/or no post baseline assessment	Date of first dose	Censored
Disease progression documented between scheduled visits	Date of disease progression	PFS event
Death due to COVID-19	Date of last adequate assessment	Censored
Death before first assessment	Date of death	PFS event
Death between adequate assessment visits	Date of death	PFS event
New systemic therapy started prior to disease progression	Date of last adequate assessment* prior to the start of subsequent antineoplastic therapy	Censored
Treatment discontinuation for undocumented disease progression after the last adequate assessment	Date of last adequate assessment	Censored
No documented disease progression or death	Date of last adequate assessment	Censored

For patients in cohort 4, not evaluable by RECIST so being assessed by CA-125 criteria, the below table describes the criteria for defining progression and the date to be used in PFS derivation.

GCIG-Rustin-modified definition of progressive disease according to CA-125 definition		
	Definition of progression	Date of progression
Patients with elevated CA-125 before treatment and normalisation of CA-125 during treatment	CA-125 \geq 2 X ULN documented on 2 occasions**	Date CA-125 is first elevated to \geq 2 X ULN
Patients with elevated CA-125 pre-treatment that never normalises	CA-125 \geq 2 X nadir value on 2 occasions**	Date CA-125 is first elevated to \geq 2 X nadir value

Document: T:\sas\Debiopharm\Debio_1143\CZA60507\Biostatistics\Documentation\SAP\SAP Text\5
 Author: [REDACTED] Version Number: 5.0
 Version Date: 19APR2022

Template No.: CS_TP_BS016 Revision 5 Reference: CS_WI_BS005
 Effective Date: 01Apr2018

Copyright © 2009, 2010, 2012, 2016, 2018 IQVIA. All rights reserved. The contents of this document are confidential and proprietary to IQVIA Holdings Inc. and its subsidiaries. Unauthorized use, disclosure or reproduction is strictly prohibited.

Patients with CA-125 in normal range pre-treatment	CA-125 ≥ 2 X ULN documented on 2 occasions**	Date CA-125 is first elevated to ≥ 2 X ULN

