----------------------------------------------------	---------------------------------------------------	-------------------------------------------------

**Repeat CA-125 anytime but normally not less than 1 week after the first elevated CA-125 level. CA-125 levels in samples obtained after administration of mouse antibodies or within 4 weeks after surgery or paracentesis should not be considered.

In patients for whom response to treatment is evaluated by both RECIST and CA-125 criteria, the RECIST evaluation will be used.

The median PFS and the PFS rate at each months will be derived from the Kaplan-Meier curves, as described in section 7.6.

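### Cohort 4: the SAP puts RECIST ahead of CA-125 where protocol Appendix C takes the earlier date, does not declare it, and scores CA-125 response with no condition that imaging is free of progression

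*SAP*

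**What the plan says.** **Patients assessed by both methods.** Protocol Appendix C (GCIG CA-125 criteria) ends with the rule that "the date of response and progression will be the earliest date of the two methods". SAP 17.2.1.5 carries over the same CA-125 progression table and footnote, then closes differently: "In patients for whom response to treatment is evaluated by both RECIST and CA-125 criteria, the RECIST evaluation will be used". SAP 4.3, the list of changes from the protocol, does not mention this.

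**Other protocol text on when CA-125 applies.** Section 11.4.1.1 reads "Response according to RECIST version 1.1 (38) or GCIG criteria (39) (Cohort 4 for RECIST non-evaluable patients) will be assessed". Section 8.2.1.2 uses the marker "in patients without RECIST measurable disease in ovarian cancer" and related tumours. Section 8.3.2.1 refers to progression "by GCIG criteria (Cohort 4, if applicable) in RECIST non-evaluable patients". These three sections describe a hierarchy with RECIST first, as the SAP does. The endpoint definition in 8.1.1.2, however, allows the two criteria together or as alternatives.

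**Patients not evaluable by RECIST.** SAP 17.2.1.5 introduces the CA-125 progression table "For patients in cohort 4, not evaluable by RECIST so being assessed by CA-125 criteria". For the primary endpoint, SAP 17.1.1 opens the CA-125 route with the clause "In the situation of lack of RECIST evaluation data (cohort 4 only", after which "confirmed objective response as per GCIG criteria will be done using CA-125 levels". The response is a fall of half or more from the pre-treatment value, held for 28 days. SAP 17.2.1.1 uses the same fall without confirmation for the futility looks. Neither section mentions imaging. Protocol 11.4.1.1 stops counting objective response once progression is documented.

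**The concern.** There are two separate problems.

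The first is an undeclared change to a secondary endpoint. Where both methods are followed, the two documents date progression differently, and the SAP's choice can only keep or postpone the event, or lose it to censoring. Patients followed by both methods are to be expected: protocol 8.2.1 repeats CA-125 on Day 1 of each cycle in Cohort 4 whenever it is elevated at baseline, and CT or MRI is scheduled for everyone.

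The second concerns the primary endpoint and the futility looks. A patient without measurable disease still has scheduled scans, and protocol 8.2.1.3 and Appendix C treat a new lesion as progression. The SAP does not say what happens when CA-125 falls while a scan shows a new lesion. With boundaries of 0/8, at most 1/11 and at least 4/15, a single patient can change the decision for a cohort.

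**Working it through.** **1. PFS in patients assessed by both methods**

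Inputs: CA-125 on Day 1 of each 28-day cycle and imaging every 8 weeks (protocol 8.2.1); PFS in months = (event date − start date + 1)/30.4375 (SAP 17.2.1.5), which is study day/30.4375. The progression days are assumed for illustration, on the nominal schedule.

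| CA-125 PD | RECIST PD | SAP (RECIST) | Appendix C (earliest) |
|---|---|---|---|
| day 29 | day 57 | 57/30.4375 = 1.87 | 29/30.4375 = 0.95 |
| day 57 | day 113 | 113/30.4375 = 3.71 | 57/30.4375 = 1.87 |
| day 29 | day 113 | 113/30.4375 = 3.71 | 29/30.4375 = 0.95 |

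The earlier of two dates cannot exceed either one, so the SAP's event date is never earlier. If no RECIST progression, clinical progression or death follows, or if new systemic therapy starts first, the SAP's table censors the patient at the last adequate assessment. Appendix C would record an event.

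**2. The boundaries**

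Inputs: prior Beta(0.5, 0.5); futility if P(θ ≤ 0.05) > 0.20; efficacy if P(θ > 0.15) ≥ 0.80 (SAP 5.3). The posterior is Beta(0.5 + r, 0.5 + n − r).

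- 0/8: P(θ ≤ 0.05) = 0.643, stop. 1/8: 0.149, continue.
- 1/11: 0.224, stop. 2/11: 0.042, continue.
- 3/15: P(θ > 0.15) = 0.726, no claim. 4/15: 0.892, claim.

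The plan's boundaries reproduce. Protocol Table 11-1 prints 0.17 as the reference for confirmed ORR; with that value the last pair is 0.647 and 0.843, so 4/15 still holds. At each of these margins one extra counted responder reverses the decision.

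**3. How a responder with new lesions could arise**

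Take a patient with non-measurable disease and CA-125 above the GCIG entry level. Suppose CA-125 has halved on day 29 and stays down on day 57, and the week-8 scan shows a new lesion. The 28-day condition is met (57 − 29 = 28). If a patient without target lesions is taken to lack RECIST data, SAP 17.1.1 as written gives a confirmed response. Protocol 11.4.1.1 would stop counting response at the documented progression. In the same way, a first CA-125 halving on day 85, after a new lesion on day 57, satisfies the wording of SAP 17.2.1.1.

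Nothing elsewhere in the SAP supplies the missing condition explicitly. The unconfirmed best response in 17.2.1.2 stops only at new anti-neoplastic therapy. The definition of PD in 17.1 is not linked to the CA-125 rules. Duration of response (17.2.1.6) gives both a RECIST and a CA-125 start date with no order of priority.

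**4. An outer range for miscounting**

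The documents give no miscount rate, so this is an assumption. If a share m of all non-responders were miscounted, the counted rate is q = p + (1 − p)m. With confirmed and unconfirmed response treated as the same, the chance of an efficacy claim over the 8/11/15 looks at p = 5% is:

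- 0.5% with m = 0
- 4.9% with m = 5% (q = 0.0975)
- 15.7% with m = 10% (q = 0.145)

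Only patients assessed by CA-125 alone can be miscounted in this way, so the real effect should be smaller.

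**The case against.** The strongest reply is that the SAP follows the body of the protocol. Sections 8.2.1.2, 8.3.2.1 and 11.4.1.1 all reserve GCIG criteria for patients not evaluable by RECIST, and only Appendix C says otherwise. This stands. A reader might infer that the SAP simply breaches the protocol. The documents show instead a protocol that disagrees with itself and a SAP that picked one side without saying so. Changing the SAP alone would leave it in tension with 11.4.1.1.

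A reader might also infer that using CA-125 alone in RECIST non-evaluable patients contradicts Appendix C. It does not, because the earliest-date rule covers only patients evaluated by both methods. Nor is it established that PFS ignores their scans. SAP 17.1 says PD may be clinical or radiological for the analyses that follow, and the CA-125 table can be read as adding to that. What remains is an ambiguity.

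The most tempting inference is that giving RECIST priority turns patients with new lesions into responders. In patients assessed by both methods it does the opposite: a new lesion is PD, and RECIST governs. The earliest-date rule is the one that could admit such a response there. The gap exists only in RECIST non-evaluable patients, and only if a patient who has scans but no measurable lesion counts as lacking RECIST data. The SAP does not define that condition, and it nowhere says that such a patient remains a responder.

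**Conclusion.** Two limited points hold.

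First, for Cohort 4 patients evaluated by both methods, the SAP departs from Appendix C without declaring it. Each patient's PFS event is on the same date or later, or is replaced by censoring. The size depends on how far RECIST progression lags behind CA-125 progression. In the assumed examples the difference is 0.92 to 2.76 months (1.87 − 0.95; 3.71 − 0.95). It would be wrong to cap it at one scan interval, since nothing ties RECIST progression to the next scan, or to any scan.

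Second, the CA-125 response rules in SAP 17.1.1 and 17.2.1.1 lack a condition that radiological progression is absent, which protocol 11.4.1.1 implies. On one reading this could move a futility or efficacy boundary by one patient. The documents do not say how many Cohort 4 patients would be assessed by CA-125 alone.

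A reader might conclude that a false efficacy claim is likely. The documents do not support that. SAP 4.3 in version 5.0 already describes the Part B cohorts as futile, and futility stopping is binding, so if this includes Cohort 4 the 4/15 claim is out of reach. The effect that remains is on the response, PFS and duration-of-response results still to be reported for Cohort 4.

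**What to change.** 1. In SAP 17.1.1 and 17.2.1.1, count a CA-125 response only in patients without RECIST-measurable disease, and only if no radiological progression is documented up to the sample (the confirming sample, for confirmed response). Define when RECIST data are considered lacking in a patient who has scans but no measurable lesion.
2. In SAP 17.2.1.5, state that radiological progression (a new lesion or unequivocal non-target progression), clinical progression or death is also a PFS event in patients assessed by CA-125.
3. For patients evaluated by both methods, choose one rule. Either apply Appendix C's earliest date for progression, or keep RECIST priority, correct Appendix C to agree with 8.2.1.2, 8.3.2.1 and 11.4.1.1, list the change in SAP 4.3, and report earliest-of-two PFS as a sensitivity analysis.
4. Apply the same hierarchy to duration of response in SAP 17.2.1.6.

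All of this uses data already collected and changes no sample size or boundary. The cost is SAP wording, a correction to the protocol appendix if RECIST priority is kept, minor programming, and possibly a slightly shorter Cohort 4 PFS.

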17.2.1.6. Duration of response (DoR)

DoR (months) is defined as (date of the first documented disease progression or death due to any cause, whichever occurs first – date of the initial response (PR or CR) or date of first reduction of 50% in CA-125 + 1)/30. 4375. It will be calculated only for subjects with a uBOR of CR/PR or at least a 50% reduction in CA-125 levels from a pre-treatment sample. Subjects that are lost-to-follow-up before disease progression will be censored at the date of their last adequate tumour assessment (i.e. a tumour assessment not showing NE) that occur before the start of a new anti-neoplastic therapy.

The median DoR and the DoR rate will be derived from the Kaplan-Meier curves, as described in section 7.6.

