#### Part B

There will be two interim futility analyses in each cohort. The cut-off for the futility analyses is defined as the time when the last ongoing patient from the first 8/11 evaluable patients has at least 2 post-baseline tumor assessments or prematurely discontinued.

No formal interim analysis will be performed during the futility monitoring. Only the number of patients with, at least, unconfirmed responses as per RECIST v1.1 and/or GCIG criteria (if applicable) will be checked vs. the futility boundaries in each cohort independently.

Bayesian posterior probability of the unconfirmed objective rate will be used for the early stopping rules for futility.

A general confirmed response rate of 15% is considered as promising, justifying further development. This corresponds to approximately 17% unconfirmed response rate. On the other hand, 5% is considered to be the general futility response rate (unconfirmed).

Assuming a probability confidence threshold for futility stopping of 20%, and a maximum sample size of 15 patients by cohort, the futility stopping boundaries are defined for each cohort as follows:

- 0 unconfirmed response out of 8 evaluable patients for the first interim analysis and
- $\leq 1$  unconfirmed response out of 11 evaluable patients for the second interim analysis.

Consequently, if no unconfirmed objective response is documented as per RECIST v1.1 and/or GCIG criteria (if applicable) after the 8th evaluable patient is assessed, futility will then be concluded and the recruitment will be stopped in the corresponding cohort. In case at least one unconfirmed response is documented in the first 8 evaluable patients, recruitment shall continue up to 11 evaluable patients and a second futility analysis will be conducted. If at least two unconfirmed responses are documented in the first 11 evaluable patients, the recruitment will continue up to 15 evaluable patients; otherwise the recruitment will be stopped. The early stopping for futility is binding.

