3.1.2. PART B

The primary endpoint of part B is the confirmed objective response rate (ORR) as per Response Evaluation Criteria in Solid Tumor (RECIST) v1.1 and/or Gynecologic Cancer Intergroup (GCIG) criteria (Cohort 4, if applicable).

Document: T:\sas\Debiopharm\Debio_1143\CZA60507\Biostatistics\Documentation\SAP\SAP Text\V5

Author: [REDACTED]

Version Number:

5.0

Version Date:

19APR2022

Template No.: CS_TP_BS016 Revision 5

Reference: CS_WI_BS005

Effective Date: 01Apr2018

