17.2.1.2. Unconfirmed best overall response (uBOR)

The uBOR will be defined as the best response across all post-baseline tumour assessments that occur before the start of a new anti-neoplastic therapy. For example, a subject who has SD at the first assessment, PR at the second assessment, and PD at the last assessment has a BOR of PR. The order to obtain the BOR is the following: CR, PR, SD, PD, Not Evaluable (NE).

If a subject has no post-baseline tumour assessments, BOR will be NE.

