17.2.1.3. Confirmed best overall response (cBOR)

The cBOR will also be analysed. In this case, CR and PR need to be confirmed at a subsequent assessment, at least 4 weeks after the initial overall response assessment of CR/PR and before the start of a new anti-neoplastic therapy or administration of non-permitted concomitant medications. cBOR will be derived as described in the RECIST 1.1 guidance.

Overall response first time point	Overall response subsequent time point*	cBOR
CR	CR	CR
CR	PR	SD, PD or PR ^a
CR	SD	SD, if minimum criteria for SD duration met, otherwise PD
CR	PD	SD, if minimum criteria for SD duration met, otherwise PD
CR	NE	SD, if minimum criteria for SD duration met, otherwise NE
PR	CR	PR
PR	PR	PR
PR	SD	SD
PR	PD	SD, if minimum criteria for SD duration met, otherwise PD
PR	NE	SD, if minimum criteria for SD duration met, otherwise NE
NE	NE	NE

* Subsequent time point is not necessarily the direct subsequent scan (eg. PR-SD-PR will have PR as confirmed BOR)

^a If a CR is truly met at first time point, then any disease seen at a subsequent time point, even disease meeting PR criteria relative to baseline, makes the disease PD at that point (since disease must have reappeared after CR). Best response would depend on whether minimum duration for SD was met. However, sometimes ‘CR’ may be claimed when subsequent scans suggest small lesions were likely still present and in fact the patient had PR, not CR at the first time point. Under these circumstances, the original CR should be changed to PR and the best response is PR.

When SD is believed to be the best response, it must also be a minimum of 35 days after treatment day 1. If the

Document: T:\sas\Debiopharm\Debio_1143\CZA60507\Biostatistics\Documentation\SAP\SAP Text\5

Author: [REDACTED] Version Number: 5.0
Version Date: 19APR2022

Template No.: CS_TP_BS016 Revision 5
Effective Date: 01Apr2018

Reference: CS_WI_BS005

minimum time is not met, the subject’s best overall response depends on the subsequent assessments. For example, a subject who has SD at the first assessment, PD at the second assessment and does not meet the minimum duration for SD, will have a best overall response of PD. The same subject lost to follow-up after the first SD assessment would be considered NE for BOR.

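### Duration of response is computed in unconfirmed responders, a wider group than the confirmed responders of the primary endpoint; for CA-125 this contradicts protocol Appendix C and is not listed as a change

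*SAP*

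**What the plan says.** SAP 17.2.1.6 runs DoR from the initial response (or the first 50% fall in CA-125) to first documented progression or death. It sets the population as follows: "It will be calculated only for subjects with a uBOR of CR/PR", or for those whose CA-125 has fallen by at least half from its pre-treatment value. It asks for no confirmation. SAP 17.2.1.2 defines uBOR just as broadly: "The uBOR will be defined as the best response across all post-baseline tumour assessments that occur before the start of a new anti-neoplastic therapy".

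The Part B primary endpoint is confirmed ORR (protocol 8.1.1.2, SAP 3.1.2). Under SAP 17.1.1 a RECIST responder has a cBOR of PR or CR, and SAP 17.2.1.3 adds: "CR and PR need to be confirmed at a subsequent assessment, at least 4 weeks after the initial overall response assessment of CR/PR". For patients assessed by CA-125, SAP 17.1.1 says: "The response must be confirmed and maintained for at least 28 days".

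On the general definition of DoR, protocol 11.4.1.1 does not say whether the response must be confirmed. Protocol Appendix C (GCIG CA-125 criteria) does say so for CA-125: duration is defined for a patient who meets every element of the GCIG response definition, and 28-day confirmation is one of those elements.

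No DoR analysis in confirmed responders is planned. The only sensitivity analyses in SAP 17.2.4 are for OS, and the list of departures from the protocol in SAP 4.3 does not mention DoR.

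**The concern.** DoR is conditional on responding, and readers take it together with the response rate it accompanies. SAP 17.2.3.1 restricts the unconfirmed ORR analysis to futility monitoring, so the response rate estimated at the final analysis is the confirmed one, while the DoR beside it comes from a wider set of patients.

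The SAP's own illustration shows the mismatch. In 17.2.1.2, a patient with SD, then PR, then PD has an unconfirmed best response of PR and so enters the DoR curve. Under the table in 17.2.1.3, PR followed by PD gives a cBOR of SD or PD, so the same patient is a non-responder in the primary analysis.

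Two things are at stake: whether the median DoR describes the patients counted in the primary endpoint, and, for Cohort 4, whether the SAP follows the protocol's rule for CA-125 duration.

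**Working it through.** **1. The plan's own figures.** The documents give no DoR figure to reproduce. The decision boundaries can be checked, to see whether this point touches them. With the stated Beta(0.5, 0.5) prior:

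- Efficacy needs P(θ > 0.15 | r, 15) ≥ 0.8. The result is 0.892 for 4/15 and 0.726 for 3/15, so the boundary of 4 is reproduced. Protocol Table 11-1 prints 0.17 for the confirmed rate, where SAP 5.3 has 0.15; at 0.17 the values are 0.843 and 0.647, which give the same boundary.
- Futility stops if P(θ ≤ 0.05 | r, n) > 0.2. The result is 0.643 for 0/8, 0.149 for 1/8, 0.223 for 1/11 and 0.041 for 2/11, so the boundaries 0/8 and ≤1/11 are reproduced.

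None of these uses DoR.

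**2. Who is in one set and not the other** (table in SAP 17.2.1.3)

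- PR then PD: in DoR; cBOR is SD or PD. Progression is a DoR event.
- PR then SD: in DoR; cBOR is SD. No DoR event yet, and the duration may be long.
- PR then NE: in DoR; cBOR is SD or NE. If the patient is then lost to follow-up, DoR is censored at the last adequate assessment.
- A 50% fall in CA-125 that is not maintained for 28 days: in DoR; not a response under SAP 17.1.1 or protocol Appendix C.

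The footnote to the table counts PR-SD-PR as confirmed, which keeps the unconfirmed-only group smaller.

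**3. How many patients.** Protocol 11.6.3 and SAP 5.3 take 15% confirmed as promising and add: "This corresponds to approximately 17% unconfirmed response rate".

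- Share of the DoR set that is unconfirmed only: f = (0.17 − 0.15)/0.17 = 2/17 = 11.8%.
- Expected DoR set per full cohort: 15 × 0.17 = 2.55, against 15 × 0.15 = 2.25 confirmed, a difference of 0.3 patient. Over 60 patients: 10.2 against 9.0.
- Chance that a full cohort has no unconfirmed-only responder: 0.98^15 = 74%.

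**4. Effect on the median.** Confirmed responders hold a response for at least g = 28/30.4375 = 0.92 months. After g, take their DoR as exponential with median m (assumed). If every unconfirmed-only responder has had an event before the mixed median, that median solves (1 − f) × 2^(−(t − g)/(m − g)) = 0.5, so

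t = g + (m − g) × log2(2(1 − f)).

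With f = 2/17, log2(30/17) = 0.819. For m = 6: 0.92 + 5.08 × 0.819 = 5.08 months. The last column replaces the early events with an exponential DoR of median 2 months in the unconfirmed-only group, solved numerically.

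| Confirmed median m (assumed) | All progress at about the first repeat scan | Difference | Unconfirmed-only median 2 months |
|---|---|---|---|
| 4 | 3.44 | −0.56 | 3.74 |
| 6 | 5.08 | −0.92 | 5.36 |
| 9 | 7.54 | −1.46 | 7.73 |
| 12 | 10.00 | −2.00 | 10.11 |

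The share f may differ from 2/17. Over the same range of m and with early progression in all, an assumed f of 20% gives medians 1.0 to 3.6 months shorter, and 30% gives 1.6 to 5.7 months shorter.

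**5. The opposite case.** If the unconfirmed-only patients are censored at the response scan, they leave the risk set before any event and the Kaplan-Meier median is unchanged.

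**The case against.** A reader might infer that DoR under this rule is biased short because patients who fail confirmation enter as very early events. The documents do not support that as a general statement. The DoR event is progression or death, not loss of PR. A PR followed by long SD can contribute a long duration, and a patient lost after the response scan is censored. Only PR followed promptly by PD or death produces the early event. Moreover, DoR among all unconfirmed responders is a legitimate quantity and the SAP names its population openly. It is shorter only by comparison with confirmed responders, who by definition have held a response for at least four weeks.

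Other points also count against the concern. For RECIST, the SAP contradicts nothing in protocol 11.4.1.1. Disease control also uses uBOR (SAP 17.2.1.4). Both uBOR and cBOR are tabulated (17.2.3.2), swimmer plots show response durations (17.2.3.3), and a listing gives cBOR with time to progression or death (SAP 13). SAP 4.3 also refers to the futility of the Part B cohorts. A futile cohort had at most one unconfirmed responder among its first 8 or 11 evaluable patients at that decision, so a well-populated DoR curve is unlikely.

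Most of this stands, and it limits the size and direction of the effect. It does not remove the mismatch of populations. Listings and plots are no substitute for a Kaplan-Meier DoR in the responders of the primary endpoint, and none of these arguments answers the conflict with Appendix C.

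**Conclusion.** The point holds as a mismatch of populations and, for CA-125, as an unlisted departure from the protocol. DoR is likely to be shorter than in confirmed responders when confirmation fails through progression or death; otherwise the direction is open.

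The share of 2/17 rests on the documents' planning rates, not on observed data. The 0.6 to 2.0 month range rests further on assumed confirmed medians of 4 to 12 months and on early progression in every unconfirmed-only responder, so it is the unfavourable case at that share. With only two to three responders expected in a full cohort, a single patient can still move a median. The primary endpoint, the futility and efficacy boundaries and the sample size are unaffected. This is a low-priority correction to a secondary endpoint.

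**What to change.** In SAP 17.2.1.6, define the main DoR for subjects with a cBOR of CR or PR or, where CA-125 is the basis of assessment, a CA-125 response confirmed and maintained for at least 28 days as in protocol Appendix C. Start the clock at the first documentation of the response that is later confirmed. Keep the uBOR version as a supportive output, labelled as unconfirmed. If the sponsor prefers to keep the present CA-125 rule, SAP 4.3 should list it as a change from Appendix C and give the reason.

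The cost is SAP wording and an additional output. No new data are needed. The downside is a slightly smaller DoR set: 2.25 instead of 2.55 expected patients per full cohort at the planning rates.
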